1.0 STUDY OVERVIEW, PURPOSE, AND BACKGROUND

1.1 Overview

Renal cell carcinoma (RCC) is the most common type of kidney cancer, accounting for >90% of all kidney neoplasms. There will be an estimated 62,700 new diagnoses of RCC in the United States this year, as well as 14,240 deaths from this disease [1, 2]. Early stage RCCs are typically treated with surgery alone, but once distant metastases have developed, RCC is rarely curable. The typical treatment course of metastatic RCC involves cytoreductive nephrectomy followed by systemic therapy [3]. Traditional intravenous chemotherapies are not utilized due to dismal response rates [4]. For decades, the only available agents for metastatic RCC were cytokine infusions which can be difficult for patients to tolerate and sometimes require hospital admissions for administration and monitoring. In 2005, the RCC treatment paradigm began to change rapidly with the approval of tyrosine kinase inhibitors sorafenib and sunitinib. Since that time, eight other targeted therapies have also been approved for the treatment of metastatic RCC. At present, the most commonly prescribed first-line agents are oral targeted therapies[5], a group of inhibitors which are designed to target vascular endothelial growth factor (VEGF), other tyrosine kinases and mechanistic target of rapamycin (mTOR). While median overall survival data for metastatic RCC is difficult to accurately assess due to the advancement of therapy in recent years, there is a trend towards longer survival times in clinical trials. In fact, when pazopanib was studied as a first-line agent, the median OS of these patients with metastatic RCC was >2.5 years [6, 7]. There are currently seven approved oral targeted therapies for RCC, these are axitinib, cabozantinib, sunitinib, lenvatinib, sorafenib, pazopanib and everolimus; the first six agents are all tyrosine kinase inhibitors (TKIs) while everolimus is an mTOR inhibitor [2]. Immunotherapy with the PD-1 checkpoint inhibitor nivolumab was approved in 2015 and is also being used with increasing frequency for the treatment of metastatic RCC [3]. Immunotherapy and oral targeted therapy offer superior convenience to patients over RCC treatments of past decades. Patients are now able to spend more time at home and less in the health care setting. While this is clearly preferable for patients, they now have less opportunity for face-to-face interaction with their health care providers to report the side effects of their cancer treatment.

With computers and smart devices now being pervasive in American homes [8], there is a unique opportunity to exploit technology for patient side effect reporting and management. Additionally, there has been much more emphasis on patient-reported outcomes in recent years for both improved patient care and the monitoring of clinical trial outcomes [9, 10]. Electronic cancer symptom self-reporting has already been determined to be feasible and effective in cancer patients [9]. The primary goal of this project is to determine if electronic side effect monitoring, combined with software generated self-care plans, is feasible to implement in patients with metastatic RCC who are being treated with immunotherapy or oral targeted therapy. We have therefore, partnered with Carevive Systems, a software company that is committed to improving the well-being of cancer patients through the generation of personalized self-care plans.

1.2 Carevive Software

Carevive Systems, Inc. is a health information technology company whose mission is to improve clinical and quality of life outcomes for cancer patients. They build clinical practice and patient engagement tools used across the cancer continuum to help cancer centers meet quality standards tied to reimbursement and accreditation. For more about Carevive Clinical Systems, see www.carevive.com.

In this study, Carevive will deliver a link to subjects so that an online survey can be completed. The survey will occur weekly for the first 12 weeks of the study and will be spaced out to every other week thereafter. The questions will mostly focus on side effects from their cancer therapy, as well as a few questions about drug compliance and healthcare utilization. After completion of the survey, the subjects will be given a care plan with at home self-management options for drug-related toxicities.

1.3 Targeted Therapies for the Treatment of Metastatic RCC.

For decades the only effective systemic therapies available for metastatic RCC were the cytokines interferon-alpha and interleukin-2 (IL-2), and once patients failed/progressed with cytokine therapy, there were no second-line agents available to them. The treatment paradigm for metastatic RCC began to shift in 2005-2006, with the Food and Drug Administration (FDA) approval of two oral tyrosine kinase inhibitors (TKIs), sunitinib and sorafenib. TKIs work by impeding cell signaling pathways which are essential to tumor proliferation, survival and angiogenesis. Sunitinib and sorafenib were shown to enhance progression free survival (PFS) by approximately 3 and 6 months respectively, [11, 12] in metastatic RCC patients. These agents are both multikinase inhibitors that act on intracellular Raf kinases, as well as several cell surface kinases. The potential side effect profiles of these agents are broad, but most commonly include fatigue, diarrhea, nausea, hand-foot syndrome, abdominal pain and mouth sores/pain. Pazopanib, another multi-kinase TKI, was FDA approved in 2009 based on an enhanced PFS compared to placebo and subsequent studies showed non-inferiority to sunitinib [13]. Pazopanib has a similar side effect profile to the earlier TKIs, including diarrhea, nausea, decreased appetite, weight loss, fatigue, skin rash, shortness of breath, cough, and hair discoloration. In 2012, axitinib was approved for second-line use based on a 1.4 month enhanced PFS [14]. It is unique in that it selectively targets just one family of kinases; common side effects include fatigue, hand-foot syndrome, diarrhea, anorexia, nausea, vomiting, constipation and cough/dyspnea. Later in 2012, everolimus was also approved for second-line RCC therapy, with an enhanced PFS of 3 months in that setting [15]. Everolimus is an mTOR inhibitor and common side effects include fatigue, mouth sores, diarrhea, nausea, skin rash and cough. The two most recently approved oral targeted therapies, cabozantinib and lenvatinib, are both multitargeted TKIs. While cabozantinib was studied as a single-agent, lenvatinib was used in combination with everolimus [16, 17]. Common side effects of these drugs include fatigue, headache, hand-foot syndrome, diarrhea, anorexia, edema, hair discoloration, nausea, mouth sores, vomiting, abdominal pain, arthralgia, constipation and cough.

Immunotherapy is a new form of cancer treatment that has been found to be effective in a variety of cancer types over the last several years. In metastatic RCC, nivolumab, which is a monoclonal PD-

1 blocking antibody, was also approved in 2015 for second-line treatment based on an enhanced patient overall survival by 6 months [18]. Nivolumab works by blocking the interaction of PD-L1 on tumor cells and the PD-1 receptor on T cell surfaces, thereby activating the immune system against cancer cells. Nivolumab is delivered as an intravenous infusion every two weeks and is being prescribed with increasing frequency. Therefore, although it is not an orally available agent, it is prudent to include nivolumab in our study of side effect reporting and management since many metastatic RCC patients will receive this therapy at some point during the course of their treatment. The most common side effects experienced with nivolumab are fatigue, rash, diarrhea, anorexia, nausea, constipation, vomiting, cough and shortness of breath.

Given the overall side effects profiles of the TKIs, everolimus and nivolumab, we have chosen the following eleven common side effects for patient electronic reporting and self-management in this study: diarrhea, nausea, vomiting, fatigue, hand/foot syndrome, rash, abdominal pain, anorexia, mouth sores, cough and shortness of breath.

1.4 Evidence for Integration of Technology into Symptom Management in Cancer

To improve communication between patients and their cancer care providers, electronic self-reporting of symptoms had been studied and found to be effective [19, 20]. One such reporting system, ESRA-C has been shown to reduce symptom distress during cancer therapy and their updated version, the ESRA-C-II resulted in enhanced patient verbal reporting of symptom and quality of life issues [9, 21]. Our study would differ from ESRA-C in that we are looking at one specific cancer type (metastatic RCC) and we are specifically addressing symptoms related to the cancer therapy. Also our format would be delivered to the patient in their home, where they could complete it at their convenience, whereas the ESRA-C was delivered in the office waiting room prior to appointments.

1.5 PRO-CTCAE

The National Cancer Institute's Common Terminology Criteria for Adverse Events (CTCAE) is a tool designed to standardize the reporting of clinician reported adverse events (AE) during clinical trial. This exhaustive list of symptoms, physical findings, and lab abnormalities are graded using a severity scale [10]. Approximately 10% of the adverse events in the CTCAE are patient symptoms, which are conveyed from the patient to the clinician and then recorded. This second-hand method of AE reporting has been shown to be unreliable [22], with a physician tendency to under-rate patient symptoms [23]. To improve adverse event reporting, the National Cancer Institute (NCI) developed a patient-reported outcome supplement to the CTCAE, called PRO-CTCAE. PRO-CTCAE includes questions on 124 potential patient reported items. The patient directly completes the questions through either a computer interface or an automated telephone system, eliminating the need for information to pass through a clinician. Once further validation of this reliable questionnaire is done, it is intended to be used to monitor adverse events in clinical trials [10]. We will be using the format of PRO-CTCAE in our side effect surveys since it is an independently verified strategy for side effect monitoring. We will focus on the eleven common side effects listed in the previous section to prevent the surveys from being overly burdensome to our patients.

1.6 Significance and Innovation of Study

Clinician-initiated grading of treatment side effects in cancer has previously been shown to be unreliable [23]. Our intention is to implement a software program to more accurately obtain patient side effect information and to provide patients with corresponding self-care plans. Oral targeted RCC therapies and immunotherapy carry significant side effects. The goal of this project is to generate and implement self-care plans that we believe will empower our patients to perform self-care in order to minimize treatment-related side effects between visits. These care plans will include basic side effect home management but will automatically trigger our staff pharmacists with severe side effects that need immediate personal assistance. To our knowledge, this is the first study seeking to validate an RCC-treatment specific, electronic side effect reporting tool. This strategy of AE monitoring and management via an automated self-care plan has the potential to enhance self-reporting, decrease unnecessary clinic visits and telephone calls and provide overall better patient care. Additionally, to our knowledge this is the first electronic reporting system that is collecting side effect data in the PRO-CTCAE format. Utilizing the PRO-CTCAE questions will enable this software to be more readily incorporated as a reporting tool in future clinical trials

2.0. HYPOTHESES AND AIMS

2.1. Overall Hypothesis

We hypothesize that Carevive software, which monitors treatment-related toxicities and then generates self-care management plans for these symptoms, will be feasible to implement among patients with metastatic renal cell carcinoma (RCC). Additionally we intend to collect preliminary data on treatment-related toxicities, quality of life, distress level, and drug adherence.

2.2. Primary Aim

2.2.1. Assess the feasibility of Carevive software implementation for at-home monitoring and management of treatment-related toxicities from oral targeted agents/immunotherapy among patients with metastatic RCC.

- To determine the demand for this intervention by examining the number and percentage of subjects with RCC who 1) use Carevive software to report their treatment-related symptoms; and 2) utilize the Carevive software generated care plan for management of their treatment-related toxicities.
- To determine the practicality of the intervention, by analyzing the reasons why subjects fail to self-report treatment-related toxicities or utilize software generated care plans after enrollment.
- To assess the acceptability of this intervention with validated patient reported usability scores of the software.
- To determine potential implementation obstacles of the intervention, by assessing the reasons eligible study candidates decline participation.

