6.0. METHODS AND STUDY PROCEDURES

6.1 Overview of Study:

We will conduct a phase II, single-arm clinical trial to assess the feasibility of reporting and managing side effects from oral targeted therapy or immunotherapy, through Carevive software, in patients who have advanced RCC. The study will begin when the consented subject starts a new therapy, either an oral targeted agent (pazopanib, sunitinib, axitinib, cabozantinib, lenvatinib, everolimus) or infusional immunotherapy (nivolumab), and will continue for a duration of 48 weeks or until drug is permanently discontinued by their primary oncologist. All study subjects will be asked to log their symptoms through Carevive software weekly for 12 weeks and then every other week for the next 36 weeks. Based on their symptoms, subjects will receive self-management instructions through the software (if applicable). Subjects will also be asked to monitor their medication compliance and health care utilization through the Carevive software once every four weeks for the length of the study. In addition, subjects will be asked to fill out a survey at their medical oncology office visits approximately every 3 months. This survey will include a distress assessment and a quality of life questionnaire. During these visits, a clinician will formally assess the subject's medication related adverse events. At the end of the study, the subject will be asked to fill out an in-office survey rating the usability of the Carevive software. On study completion, the subject's electronic medical record will be reviewed to determine health care utilization and oral targeted therapy refill history during the study period.

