12.1.1 Carevive Survey Usage Rates

Carevive software will track subject compliance with survey login and whether they access the generated care plans. The clinical team will be notified if a subject misses a login after failing to respond to a reminder notification.

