12.1.2 Reasons Participants Do Not Complete Survey or Utilize Care Plans

At the following login, subject will be asked the reason they did not login in the previous time point/time points (if applicable) and why they did not access the care plan.

12.1.3 Software Usability Scoring:

At the 48 week time point or at the point of subject withdrawal from study, they will be asked to take the System Usability Scale [25]. This is a 10 question survey where responses range from "Strongly Disagree" to "Strongly Agree," which are ranked with corresponding numbers. The survey provides us with a score of between 0 and 40 which is then multiplied by 2.5 to convert to a scale of 0 to 100. A SUS score above a 68 would be considered above average and anything below 68 is below average [25].

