15.0. DATA ANALYSIS AND MONITORING

15.1 Primary Outcomes:

Primary Aim 1: *To evaluate the feasibility and usability of symptom monitoring and management with Carevive software.* Specifically, we will determine the demand for this intervention by calculating the rate of compliance. For example, in the case of monthly compliance, the

proportion of subjects who log in at least once during this time frame will be reported. The threshold criteria for compliance based on previous studies [29-30], will be a monthly compliance of 75% (ie. during each month, an average of at least 75% of the subjects completed at least one Carevive survey). Compliance will be determined for both survey completion and access of generated care plans. A sample size of 50 subjects produces a two-sided 95% confidence interval with a width of 0.254 for a point estimate of 75% compliance. Separately patient-level compliance will be determined, based on the proportion of logins that the subject completed during the course of the study. Reasons for noncompliance will be elicited at their subsequent login and will be reported descriptively.

Patient-rated usability, based on their SUS survey results, will also be employed as a measure of feasibility. This survey will be administered to subjects at the end of the study. A Score of >68 indicates greater than average usability [25]. We will determine overall mean usability scores, and we can produce a 95% confidence interval for the mean with a width of 0.57 standard deviations, utilizing the sample of 50 subjects.

We will also determine potential implementation obstacles for Carevive software by asking patients who fail to consent to the study to provide their reasoning. This will be reported descriptively. We will also keep track of the proportion of patients who are approached who fail to consent.

15.2 Secondary Outcomes:

Primary Aim 2: *To determine how patient-reported toxicities correlate to the subject's quality of life, distress level, drug adherence, health care utilization and physician reported toxicities.* Grading of each symptom and numeric values for quality of life, distress level, drug adherence and health care utilization rate will be determined as described in the "Data Collection and Monitoring Section." The strength of the association between symptom grade and each outcome will be measured using the Spearman's rank correlation coefficient.

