Week		0	1	2	3	4	5	6	7	8	9	10	11	12	14	16	18	20	22	24	26	28	30	32	34	36	38	40	42	44	46	48	Treat ment D/C	
PR- Symptoms	PRO-CTCAE Carevive survey	X	X	X	X	X	X	X	X	X	X	X	X	X	X	X	X	X	X	X	X	X	X	X	X	X	X	X	X	X	X	X		
PR- Healthcare Utilization	Carevive survey 7s					X				X				X		X		X		X		X		X		X		X		X		X		
PR- Drug Adherence	Adherence 7s Carevive survey					X				X				X		X		X		X		X		X		X		X		X		X		
Software Utilization	Carevive collected data		X	X	X	X	X	X	X	X	X	X	X	X	X	X	X	X	X	X	X	X	X	X	X	X	X	X	X	X	X	X	X	
Care plan Utilization	Carevive collected data		X	X	X	X	X	X	X	X	X	X	X	X	X	X	X	X	X	X	X	X	X	X	X	X	X	X	X	X	X	X	X	
Consent Failure	Recorded on screening log	X																																
Quality of Life	FKSI-DRS in office	X												X					X							X						X		
Distress Score	Distress Thermomer in office	X												X					X							X						X		
Usability	SUS																															X	X	
CD- Symptoms	CTCAE	X												X					X							X						X		
CD- Healthcare Utilization	Electronic Medical Record																															X	X	
CD- Drug Adherence	Pharmacy Confirmed																															X	X	

Abbreviation: CD = Clinician Determined, PR = Patient Reported, PRO = Patient Reported Outcomes, CTCAE = Common Terminology Criteria for Adverse Events, FKSI-DRS = Functional Assessment of Cancer Therapy: Kidney Symptom Index- Disease related Symptoms, SUS = System Usability Scale

REFERENCES

1. National Cancer Institute. Bethesda, M., . *SEER Cancer Statistics Factsheets: Kidney and Renal Pelvis Cancer*. 2016.
2. National Cancer Institute. Bethesda, M., . *Kidney Cancer (adult) -- renal cell carcinoma*. . 2016, NCI.
3. Fellner, C., *Launch of Breakthrough Therapies Will Reshape Renal Cell Carcinoma Market*. P T, 2016. **41**(8): p. 523-5.
4. Hartmann, J.T. and C. Bokemeyer, *Chemotherapy for renal cell carcinoma*. Anticancer Res, 1999. **19**(2C): p. 1541-3.
5. Cella, D. and J.L. Beaumont, *Pazopanib in the treatment of advanced renal cell carcinoma*. Ther Adv Urol, 2016. **8**(1): p. 61-9.
6. Motzer, R.J., et al., *Overall survival in renal-cell carcinoma with pazopanib versus sunitinib*. N Engl J Med, 2014. **370**(18): p. 1769-70.
7. Klapper, J.A., et al., *High-dose interleukin-2 for the treatment of metastatic renal cell carcinoma : a retrospective analysis of response and survival in patients treated in the surgery branch at the National Cancer Institute between 1986 and 2006*. Cancer, 2008. **113**(2): p. 293-301.

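### The primary aim asks how many subjects use the care plan to manage toxicities, but the plan measures only access to it, which is at best an upper bound on use

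*Combined protocol and SAP*

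**What the plan says.** The demand objective in section 2.2.1 has two parts: how many subjects report symptoms through the software, and how many "utilize the Carevive software generated care plan for management of their treatment-related toxicities". The practicality objective in the same section asks why subjects fail to do either.

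The measurement sections speak of access:

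- Section 12.1.1: "Carevive software will track subject compliance with survey login and whether they access the generated care plans".
- Section 15.1: "Compliance will be determined for both survey completion and access of generated care plans". The sentences before it give a 75% monthly threshold, illustrated by completion of at least one survey in the month.
- Section 12.1.2 is headed "Reasons Participants Do Not Complete Survey or Utilize Care Plans", but its care-plan question is "why they did not access the care plan".
- The schedule of assessments, after section 15.2, calls the row "Care plan Utilization" and gives data collected by Carevive as its source.

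On survey content, section 1.2 says the questions mostly concern side effects, "as well as a few questions about drug compliance and healthcare utilization". Section 6.1 makes self-management instructions conditional on the subject's symptoms.

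**The concern.** Accessing a plan and using it to manage a toxicity are different events, and the aim is worded as the second. Section 1.6 explains why the second matters: the care plans are meant to help patients look after themselves and so reduce side effects between visits. If access is the only quantity collected, the second part of the demand question has no direct answer.

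The practicality objective is affected too. A subject who accessed a plan and then found the advice unclear, unhelpful or too burdensome is asked nothing under section 12.1.2, so those reasons are lost. They are arguably the most useful ones for revising the software. They also cannot be recovered from access logs after the trial.

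**Working it through.** **1. The plan's own figure.** Section 15.1 gives n = 50, a point estimate of 75%, and a two-sided 95% interval of width 0.254. With x = 50 × 0.75 = 37.5, the exact (Clopper-Pearson) limits are:

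- lower: the 0.025 quantile of Beta(x, n − x + 1) = Beta(37.5, 13.5) = 0.6074
- upper: the 0.975 quantile of Beta(x + 1, n − x) = Beta(38.5, 12.5) = 0.8616
- width: 0.8616 − 0.6074 = 0.2542

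This matches 0.254. The figure is sound for any proportion of 75% among 50 subjects. It does not bear on whether that proportion is access or use.

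**2. Aim against measure.**

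| Place | Term | What is captured |
|---|---|---|
| 2.2.1, demand | utilize, for management | use of the plan |
| 2.2.1, practicality | reasons for failing to utilize | reasons for non-use |
| 12.1.1 | access | software log |
| 12.1.2 | utilize (heading), access (question) | reasons for non-access |
| 15.1 | access | compliance rate |
| Schedule | utilization | data collected by Carevive |

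The limit to access comes from 12.1.1 and 15.1. The schedule row does not itself mention access; it attaches the word utilization to the software data.

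**3. Could another source supply use?**

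- Carevive surveys (1.2, 6.5, 12.3.1, 12.3.5, 12.3.6): symptoms, drug adherence and health care utilization. No item on following the plan is described.
- Office visits (6.6): clinician toxicity grades, quality of life and distress.
- System Usability Scale (6.7, 12.1.3): a single rating at week 48 or withdrawal that covers the software and the care plans. It measures usability, not use.
- Record review (12.3.5, 12.3.6): refill history, calls to oncology providers and oncologist visits. Calling is one action a plan may advise, but a call count does not show whether the plan prompted it, and home measures leave no trace there.

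None of these measures use of the advice.

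**4. What access says about use.** Let A be the proportion who access a plan and q the share of those who use it. Assume that a plan cannot be used without being accessed, and take both proportions on the same denominator. Then use U = A × q with 0 ≤ q ≤ 1, so U ≤ A. At A = 0.75, U lies between 0 and 0.75 and equals 0.75 only if q = 1. The documents give no value for q, so the range cannot be narrowed.

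**5. Denominator.** Section 1.2 reads as if a plan follows every survey, whereas section 6.1 makes instructions conditional on symptoms. If some surveys generate no plan, an access rate over all 50 subjects mixes subjects who ignored a plan with subjects who had none to access. Section 15.1 does not say which denominator applies.

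**The case against.** The strongest reply is that access is a common demand measure in a single-arm feasibility study whose hypothesis (2.1) is only that the software can be implemented, and that section 15.1 names its variable openly as access. On this view utilization has simply been operationalised as access, and the fault lies in the wording of the aim, the heading of 12.1.2 and the schedule label. Much of this stands. Access is legitimate to report, and relabelling alone would remove the inconsistency. It would not answer the question the aim asks, nor recover the reasons why accessed plans went unused.

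Three further points on that side also stand.

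- The Carevive questionnaire is not reproduced in the protocol. The supportable statement is that no item on use is described, not that none exists.
- Not acting is not the same as not using. The example in 6.5 contains conditional advice, and a subject who reads it and never meets the condition has used the plan properly.
- A new item could appear at up to 30 post-baseline surveys (12 weekly plus 18 fortnightly). The protocol deliberately limits survey burden (1.5) and lists it as a risk (9.2).

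A reader might infer that the trial will present opening a page as use of the intervention. The documents do not support that: 15.1 commits to reporting access under that name, and access is nowhere defined as opening a page. A reader might also try to put a number on true use by applying an assumed follow-through share to 75%. No share is given, and any value below 100% must produce a result under 75%, so the exercise carries no information.

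**Conclusion.** The mismatch is real and moderate in size. Followed as written, the plan can report how many subjects accessed a care plan, but not how many used one to manage toxicities, and not why accessed plans went unused. Access is at best an upper bound on use. A 75% access result supports a claim about access only.

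This rests on three things: that a plan must be accessed to be used, that both proportions share a denominator, and that the protocol describes the survey content fully enough for an item on use to have been mentioned. It also reads the 75% threshold as extending from survey completion to access. Section 15.1 implies this without stating it, and nothing sets 75% as a threshold for acting on advice.

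The sample size and both precision statements in 15.1 are unaffected. The documents do not support a stronger conclusion, either that care-plan demand will be overstated by a known amount or that subjects who took no action are non-users.

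**What to change.** 1. In section 15.1 and the schedule, label the software measure care-plan access and define it (for example, what logged event counts). State the denominator as surveys, or subjects, that generated a plan.
2. Limit the 75% result for care plans to a statement about access.
3. At the next-login question already in section 12.1.2, add one branching item for subjects who accessed the previous plan: did they try any of the advice (yes / no, with reason / not needed)?
4. Report self-reported use separately and descriptively, with no threshold attached and with the not-needed answers not counted as non-use. Report the reasons alongside the reasons for non-access.

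The cost is one short item in an existing survey and one added table, with slight extra respondent burden and recall error over the one or two weeks between surveys. The item has to be in place before surveys run. If the sponsor judges the burden too high, steps 1 and 2, together with rewording the aim in 2.2.1 to access, would remove the inconsistency but leave use unmeasured.
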